#### **12.3.5 Surgery whilst receiving ibrutinib**

For any surgery or invasive procedure requiring sutures or staples for closure, ibrutinib should be stopped for at least 7 days prior to the intervention and not be restarted for at least 7 days after the procedure. Ibrutinib should be restarted at the discretion of the investigator when the surgical site is reasonably healed without serosanguineous drainage or the need for drainage tubes.

For minor procedures (i.e. such as a central line placement, needle biopsy, thoracentesis, or paracentesis) ibrutinib should be stopped at least 3 days prior to the procedure and should not be restarted for at least 3 days after the procedure. For bone marrow biopsies that are performed while the participant is on ibrutinib, it is not necessary to withhold ibrutinib for these procedures.

For investigational procedures (e.g. colonoscopy, endoscopy) consideration should be given as to whether a biopsy or other instrumentation is likely to be taken and the extent of the biopsy. If a biopsy or other instrumentation is possible ibrutinib should be stopped 3 or 7 days before the procedure and not be restarted for at least 3 or 7 days after, depending on the extent of the biopsy.

For emergency procedures, ibrutinib should be withheld after the procedure until the surgical site is reasonably healed, for at least 7 days after the urgent surgical procedure.

Participants must be provided with the advice card, provided by the CTRU, which details the circumstances where ibrutinib should be withheld for surgery. It is recommended that sites reissue the advice card annually due to the prolonged treatment period. Please remind participants of the requirement to stop ibrutinib before any surgical procedures at each clinic appointment. The increased risk of bleeding whilst taking ibrutinib should be communicated to other hospital departments as per local practice.

Where the participant has had a minor or major procedure without stopping ibrutinib a Protocol Violations eCRF should be completed.

### **12.4 Early discontinuation of treatment strategy**

In line with standard clinical care, cessation or alteration of treatment regimens at any time will be at the discretion of treating clinicians or the participants themselves.

If participants cease trial therapy for more than 4 weeks, the CI should be consulted and the participants may need to discontinue trial treatment; this does not apply to planned treatment breaks associated with the pausing ibrutinib arm.

If trial treatment is discontinued early (e.g. due to toxicity, clinician/participant choice, delay of 4 weeks), the participant should be treated off study at the discretion of the investigator.

## **12.5 Treatment post-relapse/treatment failure**

Participants randomised to the pausing ibrutinib arm who demonstrate active disease will initially resume ibrutinib treatment. Participants who present with non-responsiveness to the reintroduction of ibrutinib as evidenced by continued active disease as per the 2018 iwCLL criteria, will meet the criteria of treatment failure and this should prompt the discontinuation of ibrutinib and consideration of subsequent therapy off-study at the discretion of the local investigator.

Participants randomised to the continuous ibrutinib arm who demonstrate active disease (see Appendix 1) at any time during the trial will meet the criteria of treatment failure and should be treated off-study at the discretion of the treating clinician.

Participants in the Clinical Need Cohort should continue to receive ibrutinib at the treating clinician's discretion until this is no longer providing benefit. Non-responsiveness to continued ibrutinib, as evidenced by symptomatic active disease, should prompt the discontinuation of ibrutinib and the participant should be treated off-study at the discretion of the treating clinician.

## 13 ASSESSMENTS, SAMPLES, DATA COLLECTION AND FOLLOW UP

---

### 13.1 Local policies for COVID-19 (and / or similar)

In light of the COVID-19 pandemic (and / or similar pandemics or epidemics), sites may have implemented policies concerning the treatment and assessment of patients with CLL, for example in order to minimise hospital/clinic visits. Full blood counts are an essential component of the treatment in STATIC. If it is necessary for some of the 3-monthly follow-up appointments to be conducted remotely blood tests should be performed nearer the patient's home, for example by the GP, in order to minimise hospital/clinic visits. If implementation of these policies whilst treating STATIC participants results in a deviation from the protocol, sites should refer to Section 13.15 and follow the usual process for the reporting of protocol violations, if required.

Face-to-face clinic visits with a relevant medical professional will remain mandatory if there is evidence of a patient progressing, for example if they report noticing lymphadenopathy, in order to ensure the safety and wellbeing of participants. Furthermore, participants on the intermittent treatment pathway who are due to pause ibrutinib should continue to undergo face-to-face review to ensure there is no clinical evidence of disease before pausing treatment.

### 13.2 Submission of trial data

Informed Consent Documents will be collected via paper case report forms (CRF). QoL, Healthcare Resource Use questionnaires will be available as paper CRF's and electronic case report forms (eCRFs). All other data collection will be via Remote Data Entry (RDE) on eCRFs managed by the CTRU at the University of Leeds. Access to the live STATIC database will be provided by the CTRU following sites being authorised to open to recruitment; guidance on RDE and completing eCRFs will be provided.

The CTRU will provide an electronic copy of the paper case report forms (CRFs) required for Informed Consent Documents and QoL and Healthcare Resource Use questionnaires. Data will be completed on printed CRFs by staff at research sites and sent to the CTRU, usually via secure file transfer or standard post.

Paper QoL and Healthcare Resource Use questionnaires can be completed either in the clinic or, if a clinic visit is not possible, posted to the participant for completion at home. If they are completed by the participant in clinic, they should be sealed in an envelope before handing back to the site research team who will return them to the CTRU via post. If they have been posted to the participant for completion at home, an addressed envelope should be provided so that the questionnaires can be posted directly back to the STATIC team at the CTRU. Questionnaires completed by the participant must not be copied or retained by the site.

Electronic QoL and Healthcare Resource Use questionnaires are also available as eCRFs, and a link to the eplatform can be shared with the participant for completion. Electronic versions of questionnaires completed by the participant must not be copied or retained by the site.

Data must only be completed by personnel authorised to do so by the PI, as recorded on the trial-specific Authorised Personnel Log. Where additional documentation is required by the CTRU, e.g. hospital reports, letters etc., it is the responsibility of staff at research sites to redact all personal identifiable data prior to sending to the CTRU. Such records should only include trial number, initials and date of birth to identify the participant. The exception to this is the participant Informed Consent Document, where the participant name and signature must not be redacted. The Informed Consent Document should be returned to the CTRU via secure file transfer, where this is not possible it must be sent via post. If signed Informed Consent Documents are posted to the CTRU, they must be sent in a separate envelopes and not accompanied by clinical data or questionnaires.

Participating hospitals will be expected to maintain a file of essential trial documentation (Investigator Site File), digital versions of the site files including all essential trial documents will be provided by the CTRU.

### **13.3 Schedule of investigations**

A tabulated summary of all local and central assessments is provided in Appendix 4.

### **13.4 Samples for central analysis**

It is the responsibility of the trial site to ensure that samples are appropriately labelled in accordance with the trial procedures to conform to the 2018 Data Protection Act and General Data Protection Regulation (GDPR). Biological samples collected from participants as part of this study will be transported, stored, accessed and processed in accordance with national legislation relating to the use and storage of human tissue for research purposes and such activities shall at least meet the requirements as set out in the 2004 Human Tissue Act.

### **13.5 Registration**

Please note that assessments performed specifically for the trial must not be performed until after consent has been received. Where a test has been performed as part of local care and is within the required time-frame it does not have to be repeated but cannot be used for trial purposes until the participant has given consent.

All participants regardless of whether they enter the Randomisation Pathway or Clinical Need Cohort need to be registered. Refer to Section 10.4.3.

### **13.6 Clinical Need Cohort**

For participants entering the Clinical Need Cohort, there is no randomisation step. Initial assessments to confirm eligibility and perform a baseline for the day-today clinical care should be performed within the timeframes specified in 13.6.1. It is expected that all assessments will be performed as part of standard clinical care.

*Potential participants must attend for a face-to-face clinic appointment in order for a medically qualified doctor to assess eligibility for STATIC (even whilst policies are in place to minimise hospital visits during the COVID-19 pandemic or similar epidemic/ pandemic).*

**Any assessments performed specifically for the purposes of the trial must only be performed after full written informed consent has been obtained and the participant has been registered into the trial.**

Cardiac monitoring should be conducted, in line with standard of care. If abnormal cardiac function is identified during screening, and, in the opinion of the PI, meets the following exclusion criterion, then the participant should be excluded from the trial:

*Symptomatic cardiac failure not controlled by therapy, or unstable angina not adequately controlled by current therapy (in patients with a significant cardiac history the left ventricular function should be assessed and patients with severe impairment should be excluded)*

### 13.6.1 Eligibility and Baseline Local Investigations

Mandatory Investigation to Confirm Eligibility?	Type of Investigation	Comments
Yes	Complete Medical History	Including detailed history of CLL (including duration of treatment with ibrutinib or other BTK inhibitor (date of commencement of ibrutinib, dose, any significant periods of treatment since starting, prolonged (of a month or more) planned and unplanned periods of treatment breaks, history of treatment and how long the potential participant has been in clinical remission (minimum of preceding 12 months), other ongoing medical conditions that require treatment, concomitant medications, IGVH mutation status (if known)  Within 2 weeks prior to registration
Yes	Pregnancy test	Serum or urine HCG in women of child bearing potential within 2 weeks prior to registration
No	Complete Physical Examination, Vital Signs and Clinical Assessment of Disease	Within within 2 weeks to registration  To confirm potential participant remains in clinical remission: 
 
- No palpable lymph nodes ;
 
- no palpable spleen;
 
 
 
- B-CLL in accordance with 2018 iwCLL criteria
 
 In addition: Systolic and diastolic blood pressure, pulse rate, height, weight

Yes	Local Haematology and Biochemistry	To confirm potential participant remains in clinical remission: - ALC lymphocyte count below $5 \times 10^9/L$  Within 4 weeks prior to registration
Yes	WHO performance status	Within 4 weeks prior to registration Refer to Appendix 2.
No	Local Haematology and Biochemistry	FBC (Hb, platelets, WBC count, ANC neutrophils, ALC lymphocytes, reticulocyte count)  Within 2 weeks prior to registration
No	Local Haematology and Biochemistry	U&E's (calcium (adjusted), urea, urate, serum creatinine, calculated creatinine clearance)  Within 4 weeks prior to registration
Yes	Local Haematology and Biochemistry	LFT's (bilirubin, alkaline phosphatase, ALT or AST)  Within 4 weeks prior to registration
Yes	Hepatitis B and C	Serology for Hepatitis B and C (HBsAg, HBcAb & HCAb)  (Within 12 weeks prior to registration)
Yes	Cardiac Assessment (conducted as per SoC)	Cardiac assessments should be performed as per SoC (if formal assessments, such as an ECHO, are conducted within any time frame the results will be acceptable)
No	Blood pressure	Take/ document blood pressure and monitor participants as appropriate to ensure blood pressure is below 140/90mmHg. Participants with hypertension (either prior to the trial or emergent on treatment) should be managed according to NICE Guidelines (NG136; published August 2019)*, see Appendix 5, to keep the blood pressure below 140/90mmHg. Blood pressure should be reported on the relevant eCRF according to the (CTCAE) V5.0 grades, see Appendix 3.  *with the exception of the excluded concomitant medications listed in section 12.3.2

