### **Number of participants:**

800 participants will be randomised into the randomisation trial over a 6 year period with ~45% coming from ibrutinib-based treatment arms of the front-line CLL trial FLAIR and ~55% receiving ibrutinib off-trial (via NHS access) for previously treated for CLL. An additional cohort of ~30 patients from the ibrutinib-based treatment arms of FLAIR will be enrolled to a non-randomised Clinical Need Cohort to receive continuous ibrutinib.

**Participant population and participant entry pathway:** (Refer to protocol Section 9 for a full list of eligibility criteria).

- To be eligible for randomisation, participants aged at least 18 years with previously treated chronic lymphocytic leukaemia (CLL) will have already been treated in second or subsequent line of therapy with ibrutinib for at least 3 years and be in clinical remission, defined as no palpable lymph nodes, no palpable spleen and absolute lymphocyte count (ALC)  $<5 \times 10^9/L$ , for at least the last 12 months
- For previously treated CLL participants, the entry pathway is to be randomised to either the 'Pausing Ibrutinib' arm or 'Continuous Ibrutinib' arm
- Front-line CLL participants from the ibrutinib-based treatment arms of the FLAIR trial will have completed 6 years of ibrutinib within FLAIR and the following treatment pathways are available:
  - o Randomisation Pathway: Randomised to either the Pausing Ibrutinib or Continuous Ibrutinib arms; participants must be in clinical remission, defined as no palpable lymph nodes, no palpable spleen and absolute lymphocyte count (ALC)  $<5 \times 10^9/L$ , for at least the last 12 months.
  - o Clinical Need Cohort: Continuous Ibrutinib (non-randomised and non-comparative)

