
The strategy of intermittent treatment with a kinase inhibitor has been studied in chronic myeloid leukaemia (CML), a haematological malignancy treated with continuous oral tyrosine kinase inhibitors (TKI) such as imatinib. TKI treatment breaks in CML have been shown to be a safe and effective approach in this disease with no adverse impact on long-term disease control (15, 16). This precedent demonstrates the efficacy in haematological malignancies treated with an intermittent, as opposed to continuous TKI, which may translate to CLL treatment.

In the FLAIR trial (17) patients who still have detectable CLL after 3 years of ibrutinib-based therapy are scheduled to receive a total of 6 years of ibrutinib and then to stop treatment. It is likely that a proportion of patients will, at the end of 6 years, have a very low level of, or even undetectable, residual disease. There is a strong rationale, as explained above, for patients to consider entry into STATIC, given that patients randomised to intermittent ibrutinib will be carefully monitored and will be able to re-commence ibrutinib if their CLL begins to progress, with the expectation that many would be likely to respond upon restarting therapy.

Given that the efficacy of intermittent treatment is not proven, and continuous treatment with ibrutinib has demonstrated durable disease control in multiple studies, the Clinical Need Cohort affords patients who are concerned about pausing therapy a pathway to continue ibrutinib as it is licensed (continuous treatment) within STATIC.

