### 9.2.1 Clinical Need Cohort Inclusion Criteria

1. Meet all of the Registration Inclusion criteria
2. Currently receiving ibrutinib and nearing the end or having completed 6 years of ibrutinib treatment on FLAIR\*
3. Have signs of progressive or returning CLL after completing 6 years of ibrutinib treatment within FLAIR, but prior to entry into STATIC

\* Patients should enter STATIC on completion of treatment in FLAIR, with no break in therapy, with the exception of participants who have completed the 6 years of treatment in FLAIR prior to STATIC opening

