### 9.2.2 Clinical Need Cohort Exclusion criteria

1. Meet none of the registration exclusion criteria
2. Active Disease, as per the 2018 iwCLL criteria requiring an alternative therapy.

3. Received treatment other than ibrutinib for CLL since completing FLAIR
4. Be eligible for front-line randomisation (see section 9.3)

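### Two mandatory rows of the Clinical Need Cohort's eligibility table are worded to confirm remission, while the cohort's inclusion criteria require progressive or returning CLL

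*Protocol*

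**What the plan says.** **Entry criteria.** Section 9.2.1 item 3 makes it a condition of entry to the Clinical Need Cohort to "Have signs of progressive or returning CLL after completing 6 years of ibrutinib treatment within FLAIR, but prior to entry into STATIC". The Trial Summary (section 3) and section 8.1 describe the same group: FLAIR participants who cannot be randomised because their CLL is progressing or coming back. Section 9.2.2 item 4 lists as an exclusion "Be eligible for front-line randomisation (see section 9.3").

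**Eligibility table.** Section 13.6.1 is the cohort's own table. Its first column states whether each investigation is mandatory for confirming eligibility. Three rows matter here:

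- Medical history, marked *Yes*: the site records "how long the potential participant has been in clinical remission (minimum of preceding 12 months").
- ALC, marked *Yes*: the purpose is "To confirm potential participant remains in clinical remission", and the entry reads "ALC lymphocyte count below" 5 × 10^9/L, within 4 weeks before registration.
- "Complete Physical Examination, Vital Signs and Clinical Assessment of Disease", marked *No*: the same remission purpose is repeated, with nodes and spleen not palpable.

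**Definition of remission.** The Trial Summary gives it as "defined as no palpable lymph nodes, no palpable spleen and absolute lymphocyte count (ALC") below 5 × 10^9/L, held for at least the last 12 months.

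**Background.** Section 6.3 says that the cohort "affords patients who are concerned about pausing therapy a pathway to continue ibrutinib".

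**The concern.** The inclusion criterion selects people whose disease is coming back. The table that sites use to confirm eligibility for the same cohort asks them to show that the person is still in remission. The same remission wording appears in section 13.7.1 for the Randomisation Pathway, where it agrees with the entry criteria. In 13.6.1 it does not.

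At stake is who enters. A site working from the table could refuse a patient who meets 9.2.1, while a site working from section 9 would register that patient. The cohort's purpose is to describe safety and overall survival on continued ibrutinib, and such results are harder to interpret if sites apply entry differently. For the individual patient, entry determines whether ibrutinib continues within the trial.

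**Working it through.** The protocol states no figure to reproduce, so the check sets the sections side by side and takes three types of patient through both rules.

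**Inputs**

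| Item | Source | Content |
|---|---|---|
| Inclusion | 9.2.1 item 3 | Progressive or returning CLL required |
| Exclusion | 9.2.2 item 4 | Eligibility for front-line randomisation |
| Front-line randomisation | 9.3.1, 9.3.2 | Remission required; also barred by an ibrutinib break of more than 28 days in the last 12 months |
| Table, history row | 13.6.1, *Yes* | Refers to remission for at least 12 months |
| Table, ALC row | 13.6.1, *Yes* | Confirm remission; ALC below 5 × 10^9/L |
| Table, examination row | 13.6.1, *No* | Confirm remission; nodes and spleen not palpable |
| Remission | Trial Summary | Nodes, spleen and ALC criteria all met, for 12 months |

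**Patient A: disease returns as an ALC of 5 × 10^9/L or more.** I take this to be a sign of returning CLL. Section 9.2.1 does not define the term, but such a count ends remission as the Trial Summary defines it, and section 13.8.3 uses the same count as a trigger for restarting ibrutinib in the pausing arm. Patient A meets 9.2.1 item 3 and fails the mandatory ALC row on its number. The conflict is direct.

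**Patient B: disease returns in nodes or spleen, ALC below 5 × 10^9/L.** Patient B meets 9.2.1 item 3 and passes the number in the ALC row, which is the only mandatory numeric remission check. The node and spleen row is marked *No*. But remission needs all three components, so the purpose stated in the ALC row cannot be met. If the history row is read as a requirement, it fails too.

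**Patient C: all three remission components met for 12 months.** Patient C satisfies the table but does not meet 9.2.1 item 3. If otherwise eligible for front-line randomisation, patient C is also excluded by 9.2.2 item 4. Remission alone does not trigger that exclusion: a patient in remission with a break of more than 28 days is not eligible for randomisation under 9.3.2, so item 4 would not apply. Item 3 would still bar entry.

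**Result.** The stated purpose of the mandatory ALC row is incompatible with 9.2.1 item 3 for all three types. Its number conflicts with item 3 only for type A. No section exempts the cohort from the remission check.

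**The case against.** The best defence is that section 9 governs. Section 10.4.3 says that eligibility is assessed in line with section 9, and that the cohort's baseline assessments serve that end. Section 13.6.1 is a schedule of investigations, and the remission text sits in its comments column. The population is described consistently in the Trial Summary, 8.1 and 9.2.1, so a careful reader can see what was intended. The history row may be no more than an instruction to record a 12-month look-back.

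Much of this stands, and it rules out several stronger readings that a reader might infer:

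- *The cohort has no defined population.* Not supported: three sections agree on it.
- *Every one of the roughly 30 participants is blocked.* Not supported: type B passes the only mandatory number, the examination row is marked *No*, and the mix of presentations is not given.
- *Registering a patient against the table is an eligibility breach.* Not established: the no-waiver rule in section 9 concerns the inclusion and exclusion criteria, and the ALC limit is not among those listed for this cohort.
- *Section 6.3 sets a rival entry rule.* It is background. Its wording is looser than 9.2 and worth aligning, but it does not govern entry.

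The defence does not remove the conflict. Section 13.6 presents these assessments as the means of confirming eligibility, and the ALC row is marked mandatory for that purpose. The pointer to section 9 leads sites to a table that tests a different condition.

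**Conclusion.** The point holds as an internal contradiction between 13.6.1 and 9.2.1 item 3. It rests on the mandatory ALC row and, if the history row is read as a requirement, on that row as well. The non-mandatory examination row repeats the wording but adds no mandatory test.

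The size is limited. The cohort is planned at about 30 participants, alongside 800 randomised. At least those whose CLL returns as an ALC of 5 × 10^9/L or more would fail a mandatory row while meeting the inclusion criterion; their number cannot be derived from the protocol. The randomised comparison is unaffected, and section 19.4 rules out comparing cohort outcomes with the randomised pathway. The consequence is possible refusal of some intended patients and inconsistent entry between sites. That makes it worth correcting, but it is no threat to the primary analysis.

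Two assumptions are used: that an ALC of 5 × 10^9/L or more counts as a sign of returning CLL, and that sites treat a row marked mandatory for eligibility as a condition of entry.

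**What to change.** Reconcile 13.6.1 with 9.2.1 and 9.2.2 so that one consistent entry rule applies to the Clinical Need Cohort. The revision should cover the history, ALC and examination rows, and should state whether the 12-month remission entry in the history row is a requirement or a record. Check the cohort's eligibility eCRF for the same wording and change it to match. Align the description of the cohort in 6.3 with the reconciled rule. Which criterion stands is a clinical decision for the sponsor.

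The cost is a wording amendment to the protocol and, where needed, to one eCRF. The sample size and the randomised analysis do not change.
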